11.1.4 Visit 7 (Week 10 [± 5 days])/Post-Treatment Follow-Up Visit

The following procedures will be conducted at this visit:

- 1. Prior to conducting any evaluations, instruct the subject or their parent/legal guardian to complete the appropriate POEM.
- 2. Record any AEs (query subjects and their parents/legal guardians, "Are there any changes in your health since the last visit?").
- 3. Review concomitant medications/therapies.
- 4. Conduct a urine pregnancy test on all female subjects who are pre-menses (9 and older) and females of childbearing potential.
- 5. Perform an evaluation of the subject's TBSA affected by AD.
- 6. Perform an IGA.
- 7. Perform EASI evaluations.
- 8. Perform an evaluation of the other signs and symptoms of AD (hyper/hypopigmentation, dry skin).
- 9. Assess pruritus and sleep disturbance.
- 10. Instruct the subject or their parent/legal guardian to assess the degree to which the subject's AD was controlled in the 7 days immediately prior to the visit (i.e., the subject's assessment of AD).
- 11. Collect and review subject diary (dispensed from Visit 6 (Week 6)).
- 12. At select sites only obtain standardized representative photos (refer to the study-specific photography manual for further details). Photos taken will include a target lesion and full front/back images (please refer to photography manual for details).
- 13. Exit the subject from the study and complete the end of study eCRFs.

11.1.5 Unscheduled Visits

Additional visits may be scheduled, as necessary, to ensure the safety and wellbeing of subjects. All additional examinations should be fully documented in the source documents and on Unscheduled Visit eCRFs, as appropriate. Visits intended to fulfill scheduled visit requirements that fall outside the designated scheduled visit range, are not unscheduled visits. In these cases, the visit data will be collected and transcribed to the appropriate scheduled visit eCRF.

11.2 Evaluation of Efficacy

11.2.1 Total Body Surface Area (TBSA)

The investigator will assess the percent of TBSA (≥5% required to qualify at Screening and Baseline) affected by AD in the allowed treatment areas for each subject at Screening/Baseline and at all study visits. The percent of TBSA will be assessed by utilizing the handprint (palm including all the digits) method.

When utilizing the handprint (palm including all the digits) method to asses a subject's TBSA estimation, the outstretched hand (including all five digits adducted together) equals approximately 1% of the subject's TBSA. NOTE: The subject's hand is the hand of reference and not the assessor's hand.

11.2.2 Investigators Global Assessment

At Screening, Day 1 (Baseline), Week 1, 2, 4, 6 and 10 study visits (all visits), AD severity will be determined by the investigator/evaluator based on a global assessment of the inflammatory signs of AD. Evaluations will be graded on a static scale ranging from 0 (clear) to 4 (severe) as shown in the following table:

Score	Grade	Description	
0	Clear	No inflammatory signs of AD (no erythema, no induration/papulation, no lichenification, no oozing/crusting). Post-inflammatory hyperpigmentation and/or hypopigmentation may be present.	
1	Almost clear	Barely perceptible erythema, barely perceptible induration/papulation, and/or minimal lichenification. No oozing or crusting.	
2	Mild	Slight but definite erythema (pink), slight but definite induration/papulation, and/or slight but definite lichenification. No oozing or crusting.	
3	Moderate	Clearly perceptible erythema (dull red), clearly perceptible induration/papulation, and/or clearly perceptible lichenification. Oozing and crusting may be present.	
4	Severe	Marked erythema (deep or bright red), marked induration/papulation, and/or marked lichenification. Disease is wide-spread in extent. Oozing or crusting may be present.	

The primary efficacy variable is the IGA score at Week 6. Treatment success is defined as achieving clear to almost clear (i.e., a score of 0 or 1) and at least a 2-grade improvement in the IGA score at the end of treatment compared with Baseline.

11.2.3 Eczema Area Severity Index (EASI)

At Day 1 (Baseline), and Weeks 1, 2, 4, 6, and 10, the EASI will be calculated. The EASI is defined as a composite score based on the evaluated severity of 4 key signs of AD (i.e., erythema, infiltration/papulation, excoriation and lichenification), and the extent of disease in each of the 4 body regions (i.e., head/neck, trunk, upper limbs, and lower limbs).

The area of involvement (affected by inflammation, not including dry skin) of each of the 4 body regions will be determined and represented by a numeric coded value based on a scale from 0 to 6 as described below (the investigator is required to record the affected TBSA on the eCRF).

Score	Area of Involvement
0	No eruption
1	< 10%
2	10%-29%
3	30%-49%
4	50%-69%
5	70%-89%
6	90%-100%

The 4 body regions are assessed separately for each sign/symptom, and the average degree of severity of each sign in each of the 4 body parts is assigned a score of 0 (none) to 3 (severe) on a scale that allows half-unit increments.

Signs and Symptoms of Atopic Dermatitis

Score	Grade	Description		
Eryther	Erythema			
0	None	No erythema present		
1	Mild	Mild erythema, very light pink		
2	Moderate	Pink red clearly distinguishable perceptible erythema		
3	Severe	Bright red		
Infiltra	tion/Papulatio	n		
0	None	None		
1	Mild	Barely perceptible elevation		
2	Moderate	Clearly perceptible but not extensive		
3	Severe	Marked and extensive elevation		
Excori	ation			
0	None	None		
1	Mild	Scant evidence of excoriations with no signs of deeper skin damage (erosion, crust)		
2	Moderate	Severe linear marks of skin with some showing evidence of deeper skin injury (erosion, crust)		
3	Severe	Many erosive or crusty lesions		
Lichen	Lichenification			
0	None	None		
1	Mild	Slight thickening of the skin discernible only by touch and with skin markings minimally exaggerated		
2	Moderate	Definite thickening of the skin with skin marking exaggerated so that they form a visible crisscross pattern		
3	Severe	Thickened indurated skin with skin markings visibly portraying an exaggerated crisscross pattern		

The EASI score (range from 0 to 72) will then be calculated using the following formula:

Body Region	EASI Score	
Head/neck	(E+I+EX+L) x Area x P*	
Upper limbs	(E+I+EX+L) x Area x P*	
Trunk	(E+I+EX+L) x Area x P*	
Lower limbs	(E+I+EX+L) x Area x P*	
Total body score =	Sum of each region score	

E = erythema; I = infiltration/papulation; EX = excoriation; L = lichenification

Area is defined on a 7-point scale, where 0 = no eruption, 1 = < 10%, 2 = 10%-29%, 3 = 30%-49%, 4 = 50%-69%, 5 = 70%-89%, $6 = \ge 90\%$

^{*} Note that a value is assigned to P based on subject age as shown below:

	Head/neck	Upper limbs	Trunk	Lower limbs
≥ 8 years	0.1	0.2	0.3	0.4
< 8 years	0.2	0.2	0.3	0.3

11.2.4 Pruritus and Sleep Disturbance

At Day 1 (Baseline), and Weeks 1, 2, 4, 6, and 10, the subject or parent/legal guardian of pediatric subjects will assess pruritus and sleep disturbance on 4-point scales as described below. Subjects will be instructed to recall the severity based on a 24-hour period prior to the study visit.

Score	Grade	Description		
Pruritu	Pruritus			
0	None	None		
1	Mild	Occasional, slight itching/scratching		
2	Moderate	Constant or intermittent itching/scratching/discomfort which is not disturbing sleep		
3	Severe	Bothersome itching/scratching/discomfort which is disturbing sleep		
Sleep L	Disturbance	·		
0	None	None		
1	Mild	Occasional, few disturbances		
2	Moderate	Intermittent disturbances		
3	Severe	Bothersome and disruptive disturbances		

In addition, at the Week 1 only visit subjects or parent/legal guardian will be asked to assess how quickly relief of pruritus was experienced (if so) after study drug application was initiated. Assessment will be asked by the study site based on the below scale:

Window of Relief Experienced (Days)	Yes/No	
1 – 2 Days post first application	Yes □ No □	
3 – 4 Days post first application	Yes □ No □	
5 – 6 Days post first application	Yes □ No □	

11.2.5 Other Signs and Symptoms of AD

Other signs and symptoms of AD to be assessed by the investigator will include hyperpigmentation, hypopigmentation, and dry skin. These assessments will be performed at Baseline, and Weeks 1, 2, 4, 6, and 10. The scales used for assessing these signs and symptoms are as follows:

Score	Grade	Description		
Hypopigmentation				
0	None	No evidence		
1	Mild	Slight, barely perceptible		
2	Moderate	Definite, evident		
3	Severe	Marked, prominent		
Hyperp	pigmentation			
0	None	No evidence		
1	Mild	Slight, barely perceptible		
2	Moderate	Definite, evident		
3	Severe	Marked, prominent		
Dry Sk	Dry Skin			
0	None	No dryness		
1	Mild	Slight, but definite roughness		
2	Moderate	Definite roughness		
3	Severe	Marked roughness		

11.2.6 Subject's Assessment

At Day 1 (Baseline), and Weeks 1, 2, 4, 6, and 10, overall AD disease control will also be assessed by the subject or parent/legal guardian of pediatric subjects. The evaluation consists of a 4-point scale in which the degree to which the disease was controlled in the 7 days immediately prior to the assessment is rated.

Score	Description	
0	Complete disease control	
1	Good disease control	
2	Limited disease control	
3	Uncontrolled disease	

11.2.7 Patient-Oriented Eczema Measure (POEM)

At Day 1 (Baseline), Week 6 (end of treatment) and Week 10 (end of study), adult subjects and parents/legal guardians of pediatric subjects will complete the POEM questionnaire (see Appendix 17.3). The POEM questionnaire is a self-assessment of atopic eczema symptoms for adult subjects and for parents/legal guardians of children (11, 12). The POEM for Self-Assessment questionnaire should be completed by subjects ≥8 years of age, and the POEM for Proxy Completion should be completed by parents/legal guardians of pediatric subjects less than 8 years of age.

11.2.8 Photography

At select sites, photographs will be taken at Baseline, and at Weeks 2, 4, 6 and 10. Only subjects who provide written photographic consent for photographs will be included in photography. Reference shall be made to the photographic manual for this study.

11.3 Evaluation of Safety

11.3.1 Clinical Laboratory Tests

Blood and urine samples will be collected for routine safety laboratory tests (hematology, serum chemistry, and urinalysis) at Screening and Week 6 (or ET). Any subject with a screening laboratory abnormality that is determined by the investigator to be clinically significant must be approved for inclusion in the study by the medical monitor. All results will be reported, including abnormal results. Clinically significant changes in lab results from Screening, in the opinion of the investigator, should be reported as AEs. Clinically significant changes present at Week 6 (or ET) are to be followed to resolution or until clinically stable as determined by the investigator. If an AE should require laboratory testing, the results of the test must be obtained by the investigational center and filed in the subject's documentation.

Materials for sample collection will be provided to the investigational centers by the sponsor or central laboratory. Instructions for processing and shipping samples to the central laboratory are contained in the study-specific laboratory manual.

For all female subjects who are pre-menses (9 and older) and females of childbearing potential, a serum pregnancy test will be conducted at Screening and Week 6 (or ET). Additionally, urine pregnancy testing will be performed at all study visits (except Week 1). The results at the Screening and Baseline visits must be negative for a subject to enter the study. Materials for pregnancy testing will be provided to the investigational centers by the sponsor, CRO or central laboratory.

11.3.2 Vital Sign Measurements

Measurement of vital signs will be performed at Screening and Week 6 (or ET). After the subjects have been sitting for at least 5 minutes, systolic and diastolic blood pressures, pulse rates, respiration rates, and oral temperatures will be recorded (for younger pediatric subjects, aural or temporal temperatures will be allowed provided the same method is used across all study visits).

11.3.3 Physical Examinations

An abbreviated physical examination will be performed at Screening and Week 6 (or ET). Height and weight will be measured at both visits.

11.3.4 Adverse Events

An AE is any untoward medical occurrence in a subject or clinical investigation subject administered a medicinal product and which does not necessarily have a causal relationship with the study drug. Thus, AEs include any unfavorable and unintended illness, sign, symptom, clinically significant laboratory test abnormality, or disease temporally associated with the use of a medicinal product that has appeared or worsened during the course of the clinical study, regardless of causal relationship to the study drug(s) under study. The collection of non-serious AEs and serious AEs (SAEs) should begin following the subject's completion of the consent/assent process to participate in the study.

Descriptions of AEs will include the dates of onset and resolution, maximum severity, seriousness, action taken regarding study drug, corrective treatment, outcome, and investigator's assessment of causality. Worsening of disease will not be considered an AE unless it results in discontinuation of the subject from the study or requires medical intervention prohibited by the protocol. All AEs will be followed to resolution or until stable as determined by the investigator.

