8.2 Subject Exclusion Criteria

Subjects meeting any one of the following criteria will be excluded from the study:

1. Females who are pregnant, breast feeding, or who wish to become pregnant during the study period. Women of childbearing potential and females that are premenses (9 and older) must be willing to practice effective contraception for the duration of the study. (Effective contraception is defined as stabilized on oral contraceptive for at least 3 months, IUD, condom with spermicidal, diaphragm

¹ Pre-menses females and FOCBP include any female who has not undergone successful surgical sterilization (hysterectomy, bilateral tubal ligation or bilateral oophorectomy) or is not postmenopausal (defined as amenorrhea > 12 consecutive months; or women on hormone replacement therapy with documented plasma follicle-stimulating hormone level > 35mLU/mL). Even women who are using oral, implanted, or injectable contraceptive hormones, an intrauterine device, barrier methods (diaphragm, condoms, spermicidal) to prevent pregnancy, practicing abstinence or where partner is sterile (e.g., vasectomy), should be considered to be of child bearing potential.

² Urine pregnancy tests must have a minimum sensitivity of 25mIU HCG/mL of urine and must be performed within 72 hours prior to the start of study drug. Kits will be provided by the CRO/designee.

with spermicidal, implant, Nuvaring, injection, transdermal patch or abstinence.) Females on birth control must have taken the same type for at least three months prior to entering the study and must not change type during the study. Those who have used any hormonal contraception in the past must have discontinued usage at least three months prior to the start of the study.

- 2. Active cutaneous bacterial or viral infection in any treatment area at Baseline (e.g., clinically infected AD).
- 3. Sunburn, extensive scarring, extensive tattoo, or pigmented lesion(s) in any treatment area at Baseline, which would interfere with evaluations.
- 4. History of confounding skin conditions (e.g., psoriasis, rosacea, erythroderma, or ichthyosis, other than ichthyosis vulgaris).
- 5. History or presence of:
 - a. Basal/squamous cell carcinoma of skin and/or melanoma treated within the past 2 years
 - b. carcinoma of cervix effectively treated less than 5 years ago
 - c. immunological deficiencies or diseases, HIV, or serious recurrent infection

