 - d. clinically significant severe renal insufficiency or severe hepatic disorders
- 6. Current serious infection (including any skin infection).
- 7. Failure to respond to topical pimecrolimus/tacrolimus.
- 8. Use within 1 month prior to Baseline and/or expected use during the study:
 - a. oral or injectable corticosteroids
 - b. ultraviolet (UV) A/UVB therapy
 - c. psoralen plus UVA therapy
 - d. tanning booths
 - e. nonprescription UV light sources
 - f. systemic immunomodulators (except biologics, see #14(a)) or immunosuppressive therapies
 - g. interferon
 - h. cytotoxic drugs
 - i. oral tacrolimus
- 9. Use within 14 days prior to Baseline and/or expected use during the study (in the affected area(s)):
 - a. medicated topical products (e.g., containing urea, salicylic acid, ammonium lactate)
 - b. topical antibiotics
 - c. calcipotriene or other vitamin D preparations (stable dose of Vitamin D use is allowed)
 - d. topical retinoids

- e. topical antihistamines
- f. topical corticosteroids (other than hydrocortisone, see #12)
- g. nonsteroidal topical prescription products for atopic dermatitis (e.g., Eucrisa)
- h. other topical prescription products
 - inhalation steroids and/or systemic antihistamines are allowed, as long as subjects are on stable dose for at least 2 weeks before Baseline
- 10. Subjects who are on an unstable dose of opioids, or who plan to start using opioids during the course of the study (stable dose is allowed, as long as it remains unchanged during the course of the study).
- 11. Use of systemic/oral antibiotics within 14 days of Baseline visit (oral antibiotics are permitted during the study [postbaseline]).
- 12. Use of 1% hydrocortisone cream within 3 days prior to Baseline and/or expected use during the study (in the affected area(s)).
- 13. Use of any nonmedicated topical product (e.g., sunscreens, lotions, creams, bland emollients) the morning of the Baseline.
- 14. Has received systemic treatment for the skin, including but not limited to:
 - a. For existing or new biologic agents (e.g., Stelara, Dupixent), should not be used within at least 3 months prior to baseline.
 - b. Oral psoriasis medications (e.g., Otezla) should be considered systemic therapies and should not be used within at least 4 weeks prior to baseline.

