9.4.1 Prior and Prohibited Concomitant Medications / Therapies

No systemic or topical treatments for atopic dermatitis (except for use of non-medicated allowable bland emollients) should be used during the study. If any prohibited medication is used by the subject, it must be recorded as a protocol deviation. Subjects will be encouraged to limit their exposure to sunlight and avoid tanning beds or sunlamps for the duration of their participation in the study.

The following table outlines the concomitant medications that are prohibited during the study/treatment period.

Medication	Prohibited Prior to Baseline
Systemic treatment for the skin including but not limited to:	
Biologic agents (e.g., Stelara, Dupixent)	At least 3 months prior to baseline visit
Oral psoriasis agents (e.g., Otezla)	At least 1 month prior to baseline
Oral or intravenous corticosteroids	1 month prior to baseline visit
Ultraviolet (UV)A/UVB therapy	1 month prior to baseline visit
Psoralen plus UVA therapy	1 month prior to baseline visit
Tanning booths	1 month prior to baseline visit
Nonprescription UV light sources	1 month prior to baseline visit
Systemic immunomodulators (except biologics, see Exc #13(a)) or immunosuppressive therapies	1 month prior to baseline visit
Interferon	1 month prior to baseline visit
Cytotoxic drugs	1 month prior to baseline visit
Oral tacrolimus	1 month prior to baseline visit
Medicated topical products (e.g., containing urea, salicylic acid, ammonium lactate)	14 days prior to baseline visit
Systemic/oral antibiotics*	14 days prior to baseline visit
Topical antibiotics	14 days prior to baseline visit
Calcipotriene/other vitamin D preparations (stable dose of Vitamin D use allowed)	14 days prior to baseline visit
Topical retinoids	14 days prior to baseline visit
Topical antihistamines	14 days prior to baseline visit
Topical corticosteroids (other than hydrocortisone 1%, see Exc #11)	14 days prior to baseline visit
Nonsteroidal topical prescription products for atopic dermatitis (e.g., Eucrisa)	14 days prior to baseline visit
Topical prescription products	14 days prior to baseline visit

Medication	Prohibited Prior to Baseline
1% Hydrocortisone cream	3 days prior to baseline visit
Opioids	Permitted if on stable dose at Screening/Baseline; not permitted if
	unstable dose

^{*}Systemic/oral antibiotic use during the study will be permitted at the investigator's discretion.

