9.4.2 Permitted Medications / Therapies

Non-medicated topical products, such as sunscreen and bland emollients are permitted during the screening and treatment periods, however, subjects should refrain from using these products the morning of the Baseline visit.

Inhalation steroids and inhaled/systemic antihistamines are permitted provided subjects are on a stable dose for at least 2 weeks prior to the baseline visit.

Opioids are permitted provided subjects are on a stable dose and are not willing to change the dose during the course of the study. Unstable dosing or if a subject starts using opioids during the study is not permitted.

Topical or oral antifungals may be used if antifungal treatment is indicated. Topical or oral antiviral therapy also is permitted as required.

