11.3.4.1 Serious Adverse Events

All AEs will be assessed as either serious or non-serious. An SAE or serious adverse reaction is defined as any untoward medical occurrence that at any dose:

• Results in death

- Is immediately life-threatening, (the term "life-threatening" in the definition of "serious" refers to an event in which the subject is at risk of death at the time of the event; it does not refer to an event which hypothetically might have caused death if it were more severe)
- Requires in subject hospitalization or prolongation of existing hospitalization (hospitalization for elective surgery for a baseline condition is not considered an AE)
- Results in persistent or significant disability/incapacity (permanent or substantial disruption of a person's ability to conduct normal life functions)
- Is a congenital anomaly/birth defect
- Is a medically important event that may not be immediately life-threatening or result in death or hospitalization, but may jeopardize the subject and may require medical or surgical intervention to prevent one of the above listed outcomes

Important medical events that may not have resulted in death, be life-threatening, or require hospitalization may be considered an SAE when, based upon appropriate medical judgment, they may jeopardize the subject and may require medical or surgical intervention to prevent one of the outcomes listed in this definition. Examples of such medical events include allergic bronchospasm requiring intensive treatment in an emergency room or at home, blood dyscrasias, or convulsions that do not result in inpatient hospitalization, or the development of drug dependency or drug abuse.

Hospitalization is a criterion for assessment of seriousness. To qualify as serious under the criteria of "hospitalization," a hospital admission of at least a 24-hour period is required. If a subject is retained the emergency room greater than 24 hours, but not admitted for medical care, these cases should be evaluated individually, as criteria such as "medically significant" may also apply.

Hospitalization without a medical AE should not be considered either serious or an AE. Examples include the following:

- Admission for treatment of a pre-existing condition not associated with the development of a new AE or with worsening of the pre-existing condition (e.g., for work-up of persistent pretreatment lab abnormality)

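### The rule excluding worsening of atopic dermatitis from AEs has no exception for serious events or skin infection, and conflicts with the plan's own AE, SAE and cutaneous-sign rules

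*Combined protocol and SAP*

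**What the plan says.** Section 11.3.4 (Adverse Events) first gives a broad definition. An AE includes any unfavourable illness, sign, symptom or "disease temporally associated with the use of a medicinal product that has appeared or worsened during the course of the clinical study", whatever its cause. The next paragraph narrows this for the disease under study: "Worsening of disease will not be considered an AE unless it results in discontinuation of the subject from the study or requires medical intervention prohibited".

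Whether an intervention is prohibited is settled elsewhere:

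- Section 9.4.1 bars all systemic or topical treatment of atopic dermatitis (AD) except bland emollients. Its table also lists topical antibiotics and, generically, topical prescription products. Its footnote says "Systemic/oral antibiotic use during the study will be permitted", at the investigator's discretion.
- Section 8.2, exclusion 9, bars expected on-study use of topical antibiotics and other topical prescription products on affected skin.
- Section 9.4.2 allows antifungals, topical or oral, where indicated, and adds: "Topical or oral antiviral therapy also is permitted as required".

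Three other passages bear on the same events. Section 8.2, exclusion 2, reads "Active cutaneous bacterial or viral infection in any treatment area at Baseline (e.g., clinically infected AD". Section 11.3.4.1 lists among the seriousness criteria "Requires in subject hospitalization or prolongation of existing hospitalization". Section 11.3.4.3 requires cutaneous tolerability signs and symptoms to be reported as an AE when they lead to any concomitant therapy or to discontinuation.

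**The concern.** The exclusion has two exits only: leaving the study, or needing something the protocol prohibits. Neither depends on how serious the event is or on whether the skin is infected. The drugs a site would naturally use for an infected flare are largely permitted, so the second exit may not open.

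Two things are at stake. The first is the record of on-treatment skin infection. Section 5 describes the drug as targeting T cells, and exclusions 2 and 6 screen for infection at entry. The second is expedited reporting: an admission that a site decides is not an AE might never be graded for seriousness or sent to the sponsor within 24 hours.

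**Working it through.** No arithmetic applies: the point rests on no sample size, rate or event count. The check is to take each kind of flare, in a subject who stays in the study, through the relevant rules.

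| Event | Exclusion in 11.3.4 applied first | Other rules applied first |
|---|---|---|
| Flare managed with emollients alone | Not an AE | The general definition covers a disease that worsens, but this is plainly the case the exclusion was written for |
| Flare needing any other AD treatment | AE: prohibited under 9.4.1 | AE |
| Infected flare, topical antibiotic on affected skin | AE: barred by 8.2 and 9.4.1 | AE |
| Infected flare, oral or systemic antibiotic | Not an AE if classed as worsening: permitted by the 9.4.1 footnote | AE as a new illness (11.3.4), or as a cutaneous sign needing therapy (11.3.4.3) if so classed |
| Infected flare, prescription topical antiviral or antifungal | Not an AE under 9.4.2 if classed as worsening; AE if the generic bar in 8.2 and 9.4.1 governs | AE |
| Flare admitted to hospital for at least 24 hours, managed with permitted drugs | Not an AE, so nothing to grade | SAE under 11.3.4.1, reportable within 24 hours under 11.3.4.3 |

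Four things follow.

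1. **The second exit does not track severity.** If an infected flare is classed as worsening, a topical antibiotic makes it an AE and an oral or systemic one does not.

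2. **The boundary between worsening and infection is not drawn.** Worsening of disease is undefined. Section 5 counts susceptibility to secondary infection among the features of AD, while exclusion 2 classes infected AD as an infection. The second reading is the better one, but no text requires it.

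3. **Section 11.3.4.1 supports both answers on admissions.** Its SAE definition covers any untoward occurrence and makes no exception for the study disease. Its exempt-admission example is confined to admissions with no new AE and no worsening of the pre-existing condition, so an admission for worsening falls outside it. But the section also opens by grading AEs for seriousness, and says that hospitalisation without a medical AE is neither serious nor an AE. A site that starts from 11.3.4 stops there; a site that starts from 11.3.4.1 reports.

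4. **Section 11.3.4.3 uses a different threshold.** For cutaneous tolerability signs any concomitant therapy suffices, whereas for worsening only a prohibited one does. Cutaneous tolerability is not defined against worsening, and Table 1 schedules no assessment of it.

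As to what would reveal a missed event, section 12.6.1 tabulates AEs only as recorded. Section 12.6.4 presents concomitant medications in listings, so no planned table shows anti-infective use by arm.

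**The case against.** The strongest case against is that the plan, read as a whole, already captures these events. A new bacterial, herpetic or fungal infection is an illness that has appeared, so it meets the general definition in its own right. If an antibiotic is given for the AD itself, section 9.4.1 prohibits it and the exclusion is lifted; if it is given for an infection, there is a separate illness to record. Section 11.3.4.3 reaches cutaneous signs needing any therapy. Section 11.3.4.1 does not exempt an admission for worsening, and 11.3.4.3 requires every SAE to be reported whatever its suspected cause. Section 9.4 also requires each concomitant medication to be recorded with its indication, so a course of treatment leaves a trace.

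Much of this stands. It defeats two stronger readings that a reader might infer:

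- **That the plan drops infected flares, or exempts hospitalised ones from SAE reporting.** It does neither. That result needs the exclusion to be applied first and to override the other rules, and no text gives it that priority.
- **That the comparison of infections between arms is invalid.** No infection-specific comparison is planned, sites are blinded (section 9.2), and nothing in the documents shows that labelling would differ by arm.

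What the objection does not do is settle precedence. The exclusion follows the general definition and is the more specific sentence. The argument from treatment purpose works only once a site has decided that the infection is separate from the flare, and that is the undecided question. A medication listing is not an AE record and triggers no report.

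**Conclusion.** The concern holds as an unreconciled conflict. The exclusion in 11.3.4 has no stated exception for seriousness or secondary skin infection. It conflicts with the general definition beside it, with 11.3.4.1 and with 11.3.4.3. The affected events are infected or hospitalised flares managed only with permitted drugs in a subject who stays in the study; these may or may not be recorded, depending on the section a site applies. Flares that need other AD treatment, or a topical antibiotic on affected skin, are AEs under the exclusion's own terms.

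No size can be stated. The documents give no rate of flare, infection or admission among the 348 planned subjects, and nothing on how sites would classify such events. The conclusion rests on the text alone, and on the assumption that no instruction outside the documents reviewed sets an order of precedence. The change is worth making because it protects safety capture at little cost; it does not touch the efficacy analysis.

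**What to change.** Amend the sentence in 11.3.4 so that the exclusion does not apply to any event meeting a seriousness criterion in 11.3.4.1. Add that any bacterial, viral or fungal skin infection is recorded as an AE under its own diagnosis, whether its treatment is permitted or prohibited. Align 11.3.4 with 11.3.4.3, either by using one threshold or by defining how cutaneous tolerability signs differ from worsening of AD.

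Separately, reconcile section 8.2 (exclusion 9) and the table in 9.4.1, which list topical prescription products as prohibited, with 9.4.2, which permits topical antivirals and antifungals. Which treatment rule should prevail is for the sponsor to decide; the AE rule only needs the answer to be the same in every section.

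The cost is a short protocol amendment and a matching line in the eCRF completion instructions. The downside is somewhat more AEs recorded in both arms. No visit, assessment or analysis method changes.
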